6.1.3 Other efficacy endpoints

MRI-based exploratory endpoints:

• Percent change in brain volume (PCBV) from baseline to Week 108

Definition: Longitudinal brain volume measurements are derived from MRI scans by using Structural Image Evaluation, using Normalization, of Atrophy methodology (SIENA) [Smith 2001, Smith 2002].

- Number of MRI lesions (Gd+ T1 lesions) at Week 60 and Week 108
- Cumulative number of new or enlarging T2 lesions from baseline to Week 108
- Change from baseline to Week 60 and Week 108 in the volume of MRI lesions (T2 lesions, T1 hypointense lesions)

5 December 2018, page 120/376

- Absence of MRI lesions (Gd+ T1 lesions, new or enlarging T2 lesions) at Week 60 • and Week 108
- Proportion of Gd+ lesions at baseline evolving to persistent black holes (PBHs) by • Week 108 (axonal loss)
- Change of
- Change in
- Cumulative number of ^{CCI}

Clinical exploratory endpoints (disease activity, relapses, disability progression):

- Time to first confirmed relapse Definition: Time from randomization to first confirmed relapse. Relapse definition is given in Section 6.1.1. Date of the first confirmed relapse is defined as the onset date of the first confirmed relapse.
- Absence of confirmed relapses from baseline to Weeks 60 and 108 •
- Change from baseline by visit up to Week 108 in EDSS •
- No evidence of disease activity (NEDA) status up to EOS (defined by the absence of confirmed relapse, Gd+ T1 lesions, new or enlarging T2 lesions, 12-week CDA, and annual brain volume decrease $\geq 0.4\%$ from baseline to EOS and completing treatment as planned)

Other exploratory endpoints:

- Change in MSFC Z-score from baseline by visit up to Week 108
- Change in the SDMT score from baseline by visit up to Week 108 •
- FSIO-RMS patient improvement response (clinically important difference, defined as • a reduction in the FSIQ-RMS score \geq a threshold value anchored on the PGI-S of Fatigue scale, which will be determined by a blinded analysis of the data, as described in Section 11.4);
- Change from baseline by visit up to Week 108 in fatigue-related impacts as measured • by the impact sub-scales of the FSIQ-RMS
- Change from baseline in PGI-S of Fatigue by visit up to Week 108; •
- Change from baseline in Clinician's Global Impression of Change (CGI-C) of • patient's relapsing MS by visit up to Week 108;
- Preferences for several treatment outcomes from MS subjects using the MACBETH methodology (sub-study, at selected sites only).

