1.3.2.2 Pharmacodynamics in humans

Oral administration of ponesimod dose-dependently reduces the circulating lymphocyte count in humans. The maximum reduction from baseline of approximately 65–80% is achieved after a single dose of \geq 50 mg, or 40 mg o.d. at steady state. The nadir in lymphocyte count is attained within 6–10 h following a given single dose. There is no evidence of tachyphylaxis on lymphocyte count. Peripheral blood counts of both T and B cells are reduced by ponesimod, while NK cells and neutrophils are not reduced. Food, race and gender do not appear to relevantly affect the PD of ponesimod. Upon discontinuation of ponesimod, the lymphocyte count generally returns to within the normal range within 1 week.

The magnitude of lymphocyte-count reductions seen with ponesimod in MS subjects was consistent with observations made after short-term treatment in healthy subjects. In the Phase 2 dose-finding study AC-058B201, at Week 24, the mean reductions from baseline in lymphocyte count were 49.8%, 65.3% and 68.6% in the ponesimod 10 mg, 20 mg, and 40 mg groups, respectively, compared to a mean increase of 3.3% in the placebo group. Lymphocyte counts remained stable on treatment and returned to baseline levels within 1 week following ponesimod treatment discontinuation.

More detailed information can be found in the IB [Ponesimod IB].

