3.1.2 Treatment period

This period consists of a double-blind treatment period from Day 1 to Week 108. This period starts on the day of randomization immediately after the 1st dose of study drug intake (Visit 3–Day 1 of the study) and continues until the premature discontinuation of study drug or the scheduled End-of-Treatment (EOT) at Week 108.

EOT visit: The EOT visit will take place at Week 108 or earlier in case of premature discontinuation of study drug. In all cases, the EOT visit should preferably take place 1 day, and not later than 7 days, after the last dose of study drug.

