6.1.2 Secondary efficacy endpoints

There are four secondary efficacy endpoints, which will be analyzed as per the statistical testing strategy outlined in Section 11.3.1:

- Change from baseline to Week 108 in fatigue-related symptoms as measured by the symptoms domain of the FSIQ-RMS
- Cumulative number of combined unique active lesions (CUAL) from baseline to Week 108

Definition: CUAL are new Gd+ T1 lesions plus new or enlarging T2 lesions (without double-counting of lesions).

• Time to 12-week CDA from baseline to EOS

Definition: A 12-week CDA is an increase of at least 1.5 in EDSS for subjects with a baseline EDSS score of 0.0 or an increase of at least 1.0 in EDSS for subjects with a baseline EDSS score of 1.0 to 5.0, or an increase of at least 0.5 in EDSS for subjects with a baseline EDSS score \geq 5.5 which is to be confirmed after 12 weeks.

Baseline EDSS is defined as the last EDSS score recorded prior to randomization. The initial EDSS increase, meeting the above criteria, is defined as the onset of disability accumulation.

All EDSS measurements (with or without relapse, at a scheduled or unscheduled visit) will be used to determine the onset of disability accumulation. However, EDSS scores used for confirmation of disability accumulation must be obtained at a scheduled visit (i.e., unscheduled visits cannot be used as confirmatory visits) outside any ongoing relapse. In this context, relapse duration is defined as period between start and end dates if available Ponesimod / ACT-128800 Relapsing multiple sclerosis Protocol AC-058B301, OPTIMUM Version 7 5 December 2018, page 119/376

Confidential

and limited to 90 days from onset if end date is not available or duration is longer than 90 days.

In order to confirm that the EDSS increase is persistent, all EDSS measurements between the onset and the 12-week EDSS confirmation (minus 7-day visit time-window) need to show an increase in EDSS, meeting the criteria for accumulation of disability as defined above.

• Time to 24-week CDA from baseline to EOS

Definition: A 24-week CDA is an increase of at least 1.5 in EDSS for subjects with a baseline EDSS score of 0.0 or an increase of at least 1.0 in EDSS for subjects with a baseline EDSS score of 1.0 to 5.0, or an increase of at least 0.5 in EDSS for subjects with a baseline EDSS score \geq 5.5 which is to be confirmed after 24 weeks.

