7.2.3 MRI evaluations

MRI scans will be performed at Visits 2 (Baseline), 10 (Week 60), and 14 (EOT) and at any unscheduled visit (U1, U2, etc.). If applicable, MRI scans will also be performed at the corresponding visits in the PTOP (Visits 10A and 14A). Testing at all visits may be performed up to 7 days prior to or after the visit date. In case of premature study treatment discontinuation, the MRI at EOT does not need to be performed if the EOT visit occurs within less than 4 weeks of the MRI assessment at Visit 10 (Week 60).

MRI variables include the number and volume of new and total Gd+ lesions on T1-weighted MRI scans, number of new and enlarging lesions and lesion volume on T2-weighted MRI, and global measures of loss of brain tissue.

T₁-weighted imaging before and after i.v. administration of 0.1 mmol/kg body weight (= 0.2 mL/kg) of Gd as well as PD-T2-weighted imaging will be performed. Gd may cause nausea and vomiting and in very rare cases allergic reactions that could require immediate anti-anaphylactic therapy (such as steroids, epinephrine/adrenaline, etc.).

All MRI data will be analyzed by the MIAC, c/o University Hospital Basel, Switzerland. MRI scans which are of unacceptable quality for central reading evaluation will be repeated.

Prior to the start of the study, each MRI site must be qualified by MIAC. To be qualified, each MRI site will perform a dummy scan according to the parameter settings defined in the study MRI manual (separate document) and submit the image data to the MIAC who will assess the image quality, the quality of the data transfer, and the compatibility with the electronic data processing and will qualify the site accordingly. The dummy scan will not use contrast agent and will be performed on a volunteer or patient, having signed a specific informed consent for this MRI assessment. Once qualified, each MRI site must maintain all the study-specific parameter settings unchanged throughout the study.

Detailed instructions on procedures, standardization, qualification, recording, and transfer of data, etc., will be provided in the study MRI manual (separate document).

Lesion count of MRI performed within 24 months prior to the study will be recorded on the MS history page of the eCRF. These scans will not be analyzed by the MIAC.

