7.3.5 Spirometry

Spirometry tests will be performed at Visits 2, 5, 6, 10, 14, 15, and 16 (Baseline, Week 4, Week 12, Week 60, EOT, FU1 and FU2). If applicable, spirometry tests will also be performed at Visit 14A in the PTOP. In addition, unscheduled spirometry will have to be conducted in the event of persistent respiratory symptoms (e.g., dyspnea).

Ponesimod / ACT-128800 Relapsing multiple sclerosis Protocol AC-058B301, OPTIMUM Version 7 5 December 2018, page 137/376

Confidential

Prior to randomization, spirometry can be performed at Visit 2 or at any time during the pre-randomization period. Spirometry at Visits 5, 6, 10, 15, and 16 (Week 4, 12, 60, FU1, and FU2) may be performed up to 7 days prior to or after the visit date. At Visit 14 (EOT), spirometry may be performed up to 7 days prior to the visit date but no later than 7 days after the discontinuation of study drug. It is highly recommended that all spirometry assessments are performed in the morning, preferably between 06:00 and 10:00, at approximately the same time to avoid diurnal variation. When applicable, it is also highly recommended that all spirometry assessments are performed prior to study drug intake.

Spirometry testing will consist of assessing FVC and FEV₁. Further indices, part of the collected flow-volume curves, may be explored and/or used for spirometry quality control measures. The following flow-volume curve indices will be collected at each timepoint: FEV₁; FVC; the instantaneous forced expiratory flow (FEF) at 25%, 50% and 75% of the FVC (FEF_{25%}, FEF_{50%}, FEF_{75%}, respectively); the mean FEF between 25% and 75% of the FVC (FEF_{25-75%}); and the peak exploratory flow.

Spirometry tests will be conducted according to the ATS / ERS guidelines [Miller 2005a, Miller 2005b]. A central vendor will provide equipment and detailed instructions for use, calibration and validation of spirometers. The provided spirometer must fulfill the technical requirements and recommendations for range and accuracy for forced expiratory maneuvers from the ATS/ERS guidelines [Miller 2005b]. The pulmonary function facility will ensure that the spirometer is functioning properly and is calibrated according to manufacturer instruction and ATS/ERS guidelines. A copy of the calibrations of the day of test must be stored as source documents in the subject charts at each subject visit, and a log of calibration results must be maintained at the ste.

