7.3.6 DL_{CO} sub-study

DL_{CO} will be assessed in a subset of approximately 400 subjects at selected sites with appropriate and established PFT expertise. Only subjects who consent under a separate informed consent for DL_{CO} will participate in the sub-study. The assessment will be conducted at Visits 2, 5, 6, 10, 14, 15, and 16 (Baseline, Week 4, Week 12, Week 60, EOT, FU1, and FU2). If applicable, DL_{CO} tests will also be performed at Visit 14A in the PTOP. In addition, unscheduled DL_{CO} tests may be performed at any time during the study (Visits U1, U2, etc.).

Prior to randomization, DL_{CO} can be performed at Visit 2 or at any time during the pre-randomization period. DL_{CO} at Visit 5, 6, 10, 15, and 16 (Week 4, 12, 60, FU1, and FU2) may be performed up to 7 days prior to or after the visit date. At Visit 14 (EOT), DL_{CO} may be performed up to 7 days prior to the visit date but no later than 7 days after the discontinuation of study drug.

DL_{co} tests will be performed by a PFT technician, respiratory therapist or expert or an equally experienced person according to the ATS/ERS guidelines [Miller 2005a]. DL_{co} results will be reviewed by a pulmonologist or a physician adequately trained in pulmonology. All PFT technicians or other experienced participating persons will be trained on the specific requirements and have refreshment on ATS/ERS recommendations before starting on the study and will receive additional training when non-compliance issues are identified.

DL_{co} tests will be conducted according to the ATS/ERS guidelines and will be assessed by the single breath method [Macintyre 2005]. DL_{co} efforts, up to a maximum of five, will be performed to produce at least two technically acceptable and repeatable traces (according to ATS/ERS guideline criteria; see DL_{co} manual). There must be a minimal interval of at least 4 min between each effort performed. Data from all DL_{co} efforts collected during a session will be captured in the eCRF.

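### Section 7.2.3 lets a completer's Week 108 MRI fall up to 14 days after the last dose, without the 7-day end-of-treatment limit that four other tests carry

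*Protocol*

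**What the plan says.** Section 7.2.3 schedules MRI at Baseline, Week 60 and EOT, and sets one tolerance for all of them: "Testing at all visits may be performed up to 7 days prior to or after the visit date". It does not tie the scan to the last dose. Section 3.1.2 says that "the EOT visit should preferably take place 1 day, and not later than 7 days, after the last dose of study drug"; the synopsis and the footnote on the EOT visit in Table 2 give the same outer limit.

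Four other tests have a 7-day tolerance around visits during treatment but a separate rule at EOT. Spirometry (7.3.5) may be done before the EOT visit, "but no later than 7 days after the discontinuation of study drug". DLco (7.3.6), ophthalmologic assessment (7.3.9) and OCT (7.3.10) carry the same limit.

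On reversal of effect, Section 1.3.2.2 reports that in Phase 2 lymphocyte counts "returned to baseline levels within 1 week following ponesimod treatment discontinuation". Section 5.1.5.2 also relies on recovery within one week.

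The EOT scan of a completer feeds the exploratory endpoints in Section 6.1.3 ("Number of MRI lesions (Gd+ T1 lesions) at Week 60 and Week 108", absence of lesions at those visits, and NEDA) and the secondary endpoint in Section 6.1.2, "Cumulative number of combined unique active lesions (CUAL) from baseline to Week 108".

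**The concern.** A Gd+ count is a snapshot of recent lesion activity. If the Week 108 snapshot is taken one to two weeks after the drug was stopped, part of what it records can belong to a period in which the effect of ponesimod has waned. The two allowances add up because nothing in Section 7.2.3 stops them from doing so, whereas the protocol does prevent this for four other tests.

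The endpoints most exposed are the Week 108 Gd+ count, absence of Gd+ lesions, and NEDA, where a single Gd+ lesion is disqualifying. The alpha-controlled cumulative count of combined unique active lesions (CUAL) is exposed much less, because it accumulates over the whole 108 weeks. How far results move would depend on how sites happen to book scans, which has nothing to do with the treatment comparison.

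**Working it through.** The protocol states no maximum interval from last dose to MRI, so there is no figure to reproduce. The interval follows from the windows.

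**Interval from last dose to EOT scan**
- Latest EOT visit (7 days, Section 3.1.2) + MRI tolerance (7 days, Section 7.2.3) = 14 days.
- EOT on the preferred day: 1 + 7 = 8 days.
- With the limit used for the four tests: 7 days.
- Time beyond the stated one-week lymphocyte recovery: 14 − 7 = 7 days now, 7 − 7 = 0 days with the limit.

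**Drug remaining.** With the half-life of about 32 h in Section 1.3.2.1, the fraction left after 7 days is 2^(−168/32), about 2.6%; after 14 days it is 2^(−336/32), about 0.07%.

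**Size in one subject scanned on Day 14 (upper bound).** Section 1.3.2.3 gives an 83% reduction in new Gd+ lesions versus placebo for 20 mg. If lesion formation returns at once to the placebo rate, the off-drug to on-drug rate ratio is 1/(1 − 0.83) = 5.88. With x weeks without effect and an enhancement time of L weeks, the Gd+ count is multiplied by (L − x + 5.88x)/L. The protocol gives no L, so 2 to 8 weeks is an assumption. With x = 1:

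| L (weeks) | Rate on drug 0.17 of placebo | Rate on drug 0.5 of placebo (assumption) |
|---|---|---|
| 2 | 3.44 | 1.50 |
| 4 | 2.22 | 1.25 |
| 6 | 1.81 | 1.17 |
| 8 | 1.61 | 1.12 |

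The right-hand column replaces 5.88 by 1/0.5 = 2. With half a week without effect (x = 0.5) and ratio 5.88, the multipliers for L = 2, 4 and 6 are 2.22, 1.61 and 1.41.

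**CUAL in the same subject.** One of 108 weeks at the off-drug rate adds (5.88 − 1)/108 = 4.5%. If the week is instead added on top of 108 treated weeks, the rise is 5.88/108 = 5.4%, of which 1/108 = 0.9% is simply a longer observation time. Loss of effect accounts for 4.5% either way.

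**Preferred EOT day.** The latest scan is then Day 8, one day past recovery (x = 1/7). With L = 4 the Gd+ multiplier is 1 + (4.88/7)/4 = 1.17, and CUAL rises by (4.88/7)/108 = 0.65%.

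**Trial level.** The share of late scans is not known. If 10% of ponesimod scans fell on Day 14 (assumption), mean CUAL in that arm would rise by about 0.1 × 4.5% = 0.45%.

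**The case against.** The strongest reply is that nothing stated is contradicted. The endpoints are defined at Week 108 or up to Week 108, with no on-treatment condition, and the full analysis set keeps every randomized subject. Subjects who stop early are scanned off drug on purpose in the post-treatment observation period (PTOP). A reader might infer that the protocol presents the late scan as an on-treatment result; no text does so. This stands. The point is that the permitted timing gives a poorer measurement, not that a definition is breached.

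The comparison with the capped tests also has limits. They are safety tests, and for spirometry and DLco the endpoints contrast EOT with EOS, which needs a value close to treatment. Nor do all EOT tests carry the limit: the chest X-ray (7.3.7) and skin examination (7.3.13) do not. So it would be wrong to say that MRI alone was left out.

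Three further inferences go too far:
- That post-treatment lesions are certainly counted. The documented reversal concerns lymphocyte counts; that lesion formation resumes as quickly is inferred.
- That the bias runs against ponesimod. Teriflunomide is cleared slowly if left alone, but Section 5.1.14.1 starts an 11-day accelerated elimination in all subjects at EOT, so its effect may also be falling before a late scan.
- That the whole protocol lacks a limit. Section 8.2.10 on the EOT visit was not in the text available, and the MRI manual is a separate document. The amendment rationale mentions only that certain EOT assessments may be done early, which is not a late limit.

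Finally, the multipliers stack the latest visit, the latest scan and an immediate return to the placebo rate. They describe one subject at the extreme, not the trial mean.

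**Conclusion.** The point holds as a weakness in the timing rule of Section 7.2.3; the endpoint definitions only inherit it. The 14-day interval, or 8 days with EOT on the preferred day, follows directly from the text, as does the absence in that section of a limit the protocol sets for four other tests. A scan on Days 8 to 14 can therefore include lesions formed after the ponesimod effect has waned.

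The practical consequence lies mainly with exploratory endpoints: the Week 108 Gd+ count, absence of Gd+ lesions, and NEDA. In a subject scanned on Day 14 the Gd+ count could be 1.6 to 3.4 times the on-drug value, given the Phase 2 reduction of 83%, enhancement for 8 to 2 weeks, and immediate return to the placebo rate. A reader might infer that the alpha-controlled CUAL result is materially biased; the arithmetic does not support that, since the effect is about 4.5% in that extreme subject. The primary endpoint, ARR, does not use MRI and is not touched. Neither the share of late scans nor the net direction between arms can be read from the protocol.

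**What to change.** In Section 7.2.3, state that the EOT MRI may be done from 7 days before the EOT visit and not more than 7 days after the last dose, as for spirometry, DLco, ophthalmologic examination and OCT. Check Section 8.2.10 and the MRI manual and bring them into line.

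For scans already taken later, specify before unblinding a sensitivity analysis of Week 108 Gd+ lesions and CUAL among subjects who completed treatment, leaving out EOT scans more than 7 days after the last dose. Scans in the PTOP are off drug by design and need no change.

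The cost is one sentence in the protocol and the MRI manual, one additional analysis, and a slightly tighter window for booking the scan. No assessment is added.

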6.2 Safety endpoints

Treatment-emergent period is defined as the time from first study drug intake up to 15 days (inclusive) after last study drug intake. The following safety endpoints will be analyzed:

Treatment-emergent AEs, SAEs, AEs of special interest[#], and MACE

5 December 2018, page 121/376

- AEs leading to premature discontinuation of study treatment •
- Treatment-emergent morphological ECGs abnormalities (as defined by the ECG • provider)
- Change in 12-lead ECG variables (HR, PR, QRS, QT, QTcB, QTcF) from pre-dose to • selected post-dose assessments (1h, 2h, 3h, 4h) on Day 1 and on day of re-initiation of study drug
- Notable abnormalities* for selected 12-lead ECG variables (HR, PR, QT, QTcF) at • 3-hpost-dose assessment on Day 1, Week 12, and at the re-initiation of study drug when post-dose monitoring is required
- Treatment-emergent decrease of FEV_1 or FVC > 20% from baseline values
- Treatment-emergent decrease of percent predicted FEV_1 or FVC > 20 percentage • points from baseline values
- Change in FEV₁ or FVC from baseline, absolute and % of absolute change to all • timepoints up to EOS
- Change from baseline to EOS vs change from baseline to EOT in FEV_1 or FVC • (absolute and % of predicted)
- Among subjects with a decrease of $\geq 200 \text{ mL}$ or $\geq 12\%$ in FEV₁ or FVC from baseline • to EOT, reversibility defined as a decrease of < 200 mL and < 12% in FEV₁ or FVC from baseline to last available FU
- Change in lung diffusion capacity as assessed by DL_{CO} (at selected sites only), • expressed in absolute change and % of predicted value from baseline to all timepoints up to EOS
- Change from baseline to EOS vs change from baseline to EOT in DLco (absolute and • % of predicted; at selected sites only)
- Treatment-emergent notable BP abnormalities* •
- Treatment-emergent notable laboratory abnormalities* •
- Change in body weight from baseline to EOS •
- Treatment-emergent electronic self-rated version of the Columbia-Suicide Severity • Rating Scale (eC-SSRS) suicidal ideation score of 4 or above, or a "yes" response on the eC-SSRS suicidal behavior item

[#] The selection of AEs of special interest is based on the anticipated risks of treatment with ponesimod or teriflunomide (e.g., liver enzyme abnormalities) and on the events that may be related to MS comorbidities (e.g., seizures or stroke) as described in Appendix 5; the final list of AEs of special interest will be defined in the Statistical Analysis Plan (SAP).

* The selection of notable abnormalities considered for the analyses is based on standard definitions and the anticipated risks of treatment with ponesimod or teriflunomide as described in Appendix 6; the final list of abnormalities will be defined in the SAP.

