parallel-group. TITLE Multicenter. randomized. double-blind. active-controlled, superiority study to compare the efficacy and safety of ponesimod to teriflunomide in subjects with relapsing multiple sclerosis (RMS) OPTIMUM: Oral Ponesimod vs Teriflunomide In relapsing ACRONYM **MU**ltiple sclerosis **OBJECTIVES Primary objective** To determine whether ponesimod is more efficacious than teriflunomide in terms of reducing relapses in subjects with RMS. **Secondary objectives** 1. To assess the effect of ponesimod on disability accumulation and on other aspects of multiple sclerosis (MS) disease control 2. To assess the safety and tolerability of ponesimod in subjects with RMS. Prospective. multicenter. randomized. double-blind. DESIGN parallel-group, active-controlled, Phase 3, superiority study. **Pre-randomization period** PERIODS Up to 45 days before randomization. **Treatment period** The double-blind treatment period will last for 108 weeks. It will consist of a randomization visit, visits at two, four, and 12 weeks after randomization, and 12-weekly visits thereafter. **End-of-Treatment (EOT)** The EOT visit will take place at Week 108 (or earlier in • case of premature discontinuation of study drug). In all cases, the EOT visit should take place one day after the last dose of study drug but no later than 7 days after the last dose of study drug. Subjects who have completed treatment until Week 108 • will be proposed to enroll in an extension study conducted under a separate protocol. Subjects who discontinue study drug prematurely for any reason will not be eligible for the

extension study.

PROTOCOL SYNOPSIS AC-058B301

5 December 2018, page 32/376

• Subjects who prematurely discontinue study drug treatment should be subsequently treated according to local standard of care at the investigator's discretion and will be followed in the post-treatment observation period.
Post-treatment safety follow-up (FU) period: Teriflunomide is eliminated slowly from plasma. An accelerated elimination procedure must be used by all subjects after the last dose of study drug [see Section 5.1.14]. A safety FU after the last dose of study drug is mandated.
All subjects will enter the safety FU period:

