- (16) Scheduled study medication dispensing/return procedures may be adapted according to the site practice.
- (17) All AEs and SAEs that occur after signing the Informed Consent Form and up to 30 days after study treatment discontinuation must be reported.
- (18) The EOT visit will take place at Week 108 (or earlier in case of premature discontinuation of study drug). In all cases, the EOT visit should take place 1 day after the last dose of study drug but no later than 7 days after the last dose of study drug.
- (19) Unscheduled visits may be performed at any time during the study and may include all or some of the indicated assessments, based on the judgment of the investigator.
- (20) Only if no 12-lead ECG is performed at this visit.
- (21) Only at unscheduled visits when the subject meets with the treating neurologist (but not at other unscheduled visits (e.g., conducted for repeat ALT or AST testing, repeat PFT testing,...).
- (22) For subjects not continuing in the AC-058B303 extension study, FU2 will be performed 30 to 37 days after last study drug intake. For subjects continuing in the AC-058B303 extension study, an abbreviated FU2 will be performed 23 to 37days after last study drug intake, if needed for compliance reasons. The abbreviated FU2 should include: Accelerated elimination procedure compliance review, AEs/SAEs, relapse, concomitant medications
- (23) The testing of teriflunomide plasma concentration may be conducted for women of childbearing potential and fertile male subjects, if needed to confirm that contraception may be discontinued. Teriflunomide plasma concentration can also be assessed for any subjects not entering the extension study if deemed necessary for the subject's safety, at the investigator's discretion. Testing must not be conducted earlier than i) 20 weeks after last drug intake if the subject's compliance with the accelerated elimination procedure has been assessed as sufficient [see Section 5.1.14.2]; ii) 35 weeks (i.e., 8 months) after last drug intake or EOS, whichever is last, if the subject's compliance with the accelerated elimination procedure has not been assessed as sufficient.
- (24) Only if the accelerated elimination procedure has been repeated or missing intake was completed after FU1.

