3.1.4 End-of-Study

For an individual subject, EOS is reached when treatment, safety FU, and, if applicable, PTOP have been completed:

- For subjects who completed the 108-week treatment period and enter the extension study, the EOS visit corresponds to FU visit (FU1) conducted 14–22 days after the last study drug dose or to the abbreviated FU2 visit conducted 23–37 days after the last study drug dose.
- For all other subjects, the EOS visit corresponds to the 30-day FU visit (FU2) or to the last visit of PTOP (i.e., Week 108 Visit of the PTOP), whichever is last.

EOS at study level occurs at the time all subjects have completed their EOS visits, as described above and schematically presented in Figure 1, Figure 2, and Figure 3.

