6.5.2 Pharmacodynamic endpoints

- Peripheral blood lymphocyte counts pre-dose (absolute and change from baseline counts) by visit up to Week 108
- Change from baseline to EOS vs change from baseline to EOT in lymphocyte counts (absolute and % change)
- Post-treatment lymphocyte recovery at 15 days and 30 days after study drug discontinuation

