7.3.11 Weight and height

Body weight will be measured at Visits 1 (Screening), 10 (Week 60) and 14 (EOT). In addition, unscheduled body weight measurement may be performed at any time during the study (Visits U1, U2, etc.). Body height is only measured at Visit 1 (Screening). Data will be collected in the eCRF.

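### The EOS-versus-EOT endpoints for FEV1/FVC, DLco and lymphocytes mix 2–5 weeks off drug with up to about 108 weeks, and some EOS visits do not measure them at all

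*Protocol*

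**What the plan says.** Section 6.2 compares two changes from baseline, one to EOS and one to EOT, for FEV1/FVC and for DLco ("Change from baseline to EOS vs change from baseline to EOT in"). Section 6.5.2 repeats the form: "Change from baseline to EOS vs change from baseline to EOT in lymphocyte counts".

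Section 3.1.4 defines EOS by subgroup. For completers who enter the extension, "the EOS visit corresponds to FU visit (FU1) conducted 14–22 days after the last study drug dose", or it is the abbreviated FU2 at days 23–37. "For all other subjects, the EOS visit corresponds to the 30-day FU visit (FU2) or to the last visit of PTOP", whichever is later. Section 3.1.3.2 runs the PTOP from the last dose to Week 108 after randomization.

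The Synopsis (Periods) says that subjects who stop early "should be subsequently treated according to local standard of care at the investigator's discretion", and Section 5.1.12 asks the investigator to consider other MS treatment.

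Table 2, footnote 22, limits the abbreviated visit: "The abbreviated FU2 should include: Accelerated elimination procedure compliance review, AEs/SAEs, relapse, concomitant medications".

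Section 6.2 also has an endpoint for change in body weight from baseline to EOS. Section 7.3.11 schedules weight at Screening, Week 60 and EOT only.

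**The concern.** A contrast between the last on-treatment value and a later off-treatment value is naturally read as a measure of recovery. Here the later value is taken at very different times since the last dose, so one summary combines short washout with long elapsed time and, in some subjects, a new therapy.

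For lymphocytes the protocol itself shows why a new therapy matters. Section 1.2 says S1P1 modulators lower circulating lymphocytes, and Section 1.1.4.2 lists fingolimod as an approved MS drug. A low count at Week 108 of the PTOP could therefore reflect the next drug.

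The mixing is also related to outcome. A confirmed lymphocyte count below 0.2 × 10⁹/L (Section 5.1.13.2), or a repeat-confirmed, clinically significant fall of more than 30% in FEV1 or FVC (Table 5), leads to discontinuation and so to the PTOP. Recovery is of most interest in these subjects, and their EOS can be furthest from the last dose. If discontinuation differs between arms, the arm comparison mixes drug recovery with elapsed time and later therapy.

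**Working it through.** **Check of the timings.** Section 3.1.5 gives a maximum individual duration of about 118 weeks. From the visit rules: 45/7 + 108 + 30/7 = 118.7 weeks, or 119.7 with FU2 at day 37. The visit timings are being read as the protocol intends.

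**Time from last dose to EOS (Sections 3.1.3, 3.1.4; Tables 2 and 3; Sections 7.3.5, 7.3.6).**

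| Subject | EOS visit | Time since last dose | Lung function and haematology scheduled at EOS |
|---|---|---|---|
| Completer, enters extension | FU1 | 14–22 days = 2.0–3.1 weeks | Yes |
| Completer, enters extension, elimination compliance not sufficient at FU1 | Abbreviated FU2 | 23–37 days = 3.3–5.3 weeks | None listed |
| Other completer | FU2 | 30–37 days = 4.3–5.3 weeks | Yes |
| Stopped early | Later of FU2 and PTOP Week 108 | Up to 108 weeks | Yes |

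DLco applies to the sub-study only. For early stoppers the gap is max(30 days, 108 weeks − stopping week):

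- stop at Week 12: 96 weeks
- stop at Week 24: 84 weeks
- stop at Week 60: 48 weeks
- stop at Week 84: 24 weeks

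108 weeks is 108 × 7/365.25 = 2.07 years.

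**Body weight.** Table 2 marks it at EOT and as an option at unscheduled visits, not at FU1 or FU2. Table 3 has no weight row. No EOS visit schedules it.

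**How many subjects.** The protocol gives no PTOP entry rate. The only related figure is the planning dropout of 15% in year 1 and 7.5% in year 2 (Synopsis, sample size). Over 104 weeks: 1 − 0.85 × 0.925 = 21.4%. Carried to Week 108 at a constant hazard within each year: 21.8%.

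- All of it is treatment discontinuation with PTOP follow-up: 21.8%, about 240 of 1100.
- Half of it: 10.9%, about 120 of 1100.
- All of it is leaving the study: towards 0%, since those subjects have no PTOP Week 108 value.

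Under the first case only, mean time to stopping or Week 108 is 1.795 years, so the mean gap among stoppers is (2.070 − 1.795)/0.218 = 1.26 years, about 66 weeks. A simulation on the same assumptions gives a median of about 71 weeks (quartiles 45 and 90).

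**Completers.** With a ponesimod half-life of about 32 h (Section 1.3.2.1), 14 days is 14 × 24/32 = 10.5 half-lives, leaving 0.5^10.5 = 0.07%. Their EOS is an off-drug value for ponesimod.

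**The case against.** A reader might infer that these endpoints cannot show reversibility, or that the trial cannot. The documents do not support that:

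- Section 6.5.2 has a separate lymphocyte recovery endpoint at 15 and 30 days after stopping.
- Section 6.2 has a named FEV1/FVC reversibility endpoint.
- Section 6.2 also lists FEV1/FVC and DLco change at every assessment through EOS, and both are scheduled at FU1 and FU2.
- In completers, EOS versus EOT is a clean off-drug against on-drug comparison for ponesimod.
- No text shown says that the EOS–EOT contrast is the reversibility measure.
- Subjects stopped for low lymphocytes have counts at least weekly until recovery (Section 5.1.13.2). Respiratory follow-up continues until changes are no longer clinically relevant (Section 5.1.13.3).
- Section 5.1.12 discourages new immunomodulatory therapy in the first 15 days and before accelerated elimination, which limits contamination at FU1.
- Safety endpoints are mainly descriptive. Section 11.3.5.3 and the SAP were not available and may assign visits.

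All of this lowers the stakes, but it does not remove the defect. DLco has no other named reversibility endpoint. The FEV1/FVC endpoint uses the last available follow-up, which is not defined in the text shown and could also be read as the PTOP Week 108 visit. The EOS rule and the endpoints that use it are both fixed in the protocol.

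A second tempting inference is that later MS drugs distort lung function. No section shown supports such an effect, so for FEV1/FVC and DLco the concern is elapsed time.

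**Conclusion.** The point holds as a defect of definition. As written, the EOS–EOT contrasts for FEV1/FVC, DLco and lymphocytes pool about 2–5 weeks off drug with up to about 108 weeks, possibly on another MS therapy. They have no scheduled value where EOS is the abbreviated FU2. The contrast is mixed in timing, not incapable of showing reversibility. The body weight endpoint names a visit at which weight is not scheduled.

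The per-subject timing gap follows directly from the visit rules. The share of subjects does not: about 22% is an upper illustration that equates planning dropout with stopping drug and staying in the PTOP, and the figure falls towards 0% if dropout means leaving the study. The 66- and 71-week figures rest on the same reading. The primary endpoint, type I error and power are unaffected.

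**What to change.** - In Sections 6.2 and 6.5.2, and the matching Synopsis entries, define the contrasts as change from baseline at FU1 (days 14–22) and, where done, FU2 (days 30–37) versus change at EOT.
- Anchor the FEV1/FVC reversibility endpoint to the same visits.
- Report the PTOP Week 108 values separately as descriptive, flagging those taken after a new MS drug was started. Concomitant therapy is already recorded to EOS (Section 7.1.3).
- Change the body weight endpoint to baseline to EOT.

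The cost is endpoint wording and table shells. The lung function and haematology assessments are already scheduled at EOT, FU1 and the full FU2, and weight at EOT, so no new procedure is needed. The small downside is that the long-term PTOP value moves to its own table.
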